### H.1 Analysis of clinical data

The Valiant Evo International Trial is not hypothesis driven. All endpoints will be analyzed descriptively. The limitation of the design for this study is that there are no pass/fail criteria from a statistical hypothesis testing.

All endpoints will be analyzed descriptively. Event rates corresponding to the primary endpoint of the study will be analyzed by calculating the distribution frequencies and the associated 1-sided 95% confidence limits using an exact method.

In general, qualitative parameters will be described by their distribution frequencies; quantitative parameters will be described by their mean, standard deviation, minimum, maximum, median, and number of subjects with assessable data.

The survival from all-cause mortality over one year time or longer will be described by the Kaplan-Meier survival curve and the associated Kaplan-Meier estimate will be calculated along with its standard error using the Greenwood method.

For events, such as AEs, deaths and secondary procedures, that can occur or are observed at any time during the study, no time window will be applied. For such events, an event that occurs “within 30 days” is an event that takes place between Days 0 to 30, inclusive. Similarly, an event that occurs “within 365 days” is an event occurring between Day 0 to Day 365, inclusive. Date of event onset will be used to determine when the event occurred. Day 0 is referring to the day of index procedure.

For image-based assessments, such as stent-graft endoleak, patency and device deficiencies, the following time windows will be applied for by-visit data summaries:

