Aneurysm-related mortality (ARM)	
Any death occurring within 30 days from either the initial procedure or any secondary procedure intended to treat the aneurysm will be considered ARM unless there is evidence to the contrary. Additionally, deaths occurring as a consequence of any procedure intended to treat the targeted aneurysm, aneurysm rupture, or a conversion to open repair will also be considered as ARM.
 
Ultimate adjudication of relatedness of death will be made by the Clinical Events Committee (CEC). Excluded are aneurysms in anatomic areas other than the targeted segment treated by the Valiant Evo Thoracic Stent Graft System.

Device-related secondary procedure	
Any secondary procedure that is determined by the investigator to be clearly related to any of the implanted stent graft components.
 
Ultimate adjudication of relatedness of secondary procedure will be made by the Clinical Events Committee (CEC).

Secondary procedure	Any endovascular or surgical procedure performed following the completion of the operative initial implantation procedure (thus on subsequent occasion after final closure of the last artery access site) which involves the targeted vascular segment treated by the Valiant Evo Thoracic Stent Graft System in which there is either manipulation of the existing Valiant Evo Thoracic Stent Graft, implantation of any additional stent graft devices or manipulation of covered branch(es) by implanted stent grafts.
Conversion to open surgery	
Primary Conversion: Conversion from endovascular to open repair required at the time of the original procedure, to treat the lesion intended to be treated with the Valiant Evo Thoracic Stent Graft System.
 
Secondary Conversion: Conversion from endovascular to open repair required at a time beyond the initial endovascular procedure, to treat the lesion originally treated with the Valiant Evo Thoracic Stent Graft System.

Thoracic Aortic Aneurysm rupture	
Rupture or perforation of the targeted thoracic aneurysmal sac as detected by angiography, CT scan, or direct observation at surgery or autopsy.
 
Aneurysm rupture should be reported as either procedure-

Term	Definition

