k = No. of Subjects Who Had No MDE	No. of subjects who have been in study for at least 1 day and without an MDE.	No. of subjects who have been in study for at least 91 days and without an MDE.	No. of subjects who have been in study for at least 305 days and without an MDE.

If a subject is early terminated from the study, the last day that the subject has been seen will be the duration in study, which can be the day of last follow-up, last imaging taken, an AE reported, or withdrawal from the study. If a subject is still in the study, the duration in study will be the time from index procedure to the cut off day that the database is locked or data snapshot is taken.

Subgroup analyses by-sex, by-race (based on subjects enrolled in the US only, since collection of race and ethnicity data may not be allowed outside the US as per local law and regulation), FreeFlo versus Closed Web configuration as proximal component, percutaneous access versus non-percutaneous, and by-region/study site will be performed on the primary study endpoint using descriptive statistics and reviewed for

clinical significant difference.

Secondary Endpoints

30-day Secondary Endpoint

The following secondary endpoints will be evaluated within 30 days post treatment:

- Peri-operative mortality
- All adverse events (AE) within 30 days including:
 - Major Adverse Event(s) (MAE)
 - Serious Adverse Event(s) (SAE)
- Secondary procedures
- Loss of stent graft patency at 30 day visit based on imaging findings
- Endoleaks at 30 day visit based on imaging findings

Detailed definitions of MAEs are defined in the Clinical Investigational Plan Appendix L.2.2. MAEs will be identified using codes in the Medical Dictionary for Regulatory Activities (MedDRA) provided by the Medtronic Clinical Safety group.

6-month Secondary Endpoints:

The following secondary endpoints will be evaluated:

- All-cause mortality within 183 days
- Aneurysm-Related Mortality within 183 days
- MDEs within 183 days
- All AEs within 183 days including:
 - MAEs
 - SAEs
- Secondary procedures within 183 days
- Loss of stent graft patency within 6 months based on imaging findings
- Endoleaks at 6 months based on imaging findings

- Stent graft migration at 6 months as compared to 1-month imaging
- Aneurysm expansion > 5mm at 6 months based on imaging findings relative to the 1-month visit

12-month Secondary Endpoints

The following secondary endpoints will be evaluated:

- All-cause mortality within 365 days

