- Aneurysm-Related Mortality within 365 days
- MDEs within 365 days
- All AEs within 365 days including:
 - MAEs
 - SAEs
- Secondary procedures within 365 days
- Loss of stent graft patency within 12 months based on imaging findings
- Endoleaks at 12 months based on imaging findings
- Stent graft migration at 12 months as compared to 1-month imaging
- Aneurysm expansion > 5mm at 12 months based on imaging findings relative to the 1-month visit

Secondary endpoints are to be assessed beyond 12 months. The following secondary endpoints are to be evaluated at 24, 36, 48, and 60 months:

- All-cause mortality
- Aneurysm-Related Mortality
- MDEs
- All AEs and SAEs
- Secondary procedures
- Loss of stent graft patency based on site reported imaging findings
- Endoleaks based on site reported imaging findings

- Stent graft migration as compared to 1-month imaging
- Aneurysm expansion > 5mm based on site reported imaging findings relative to the 1-month visit

Health-related quality of life outcomes are to be assessed at all scheduled follow-up visits using the EQ-5D questionnaire.

Stent graft migration will be determined by the core lab or site imaging case report from (CRF). Core lab assessment and site reported result will be analyzed separately. Aneurysm expansion will be calculated. When 1-month image is not available, the latest image taken prior to 1-month will be used for calculation.

Descriptive statistical analyses will be performed on secondary endpoints. No inferential statistical analysis is planned for secondary endpoints.

Non-image endpoints event rates such as mortality, secondary procedures, MAEs, SAEs, conversion to open surgery, and thoracic aortic aneurysm ruptures through 1 year will be calculated in the same way as the MDE rate, specified in Table 5. The event rates beyond 1 year through 5 years will be analyzed using Kaplan Meier method.

Imaging based Event Rate Calculation:

Unless otherwise specified, imaging assessment will be performed by site as well as the core lab. Assessments from the core lab will be the primary result for the PMA and PMA-s submissions and analyzed separately from those by site. Imaging based event rate will be calculated using statistical analysis windows as follows (Table 6):

Table 6: Imaging based Event Rate Calculation:

Event rate = m/n	At 1 Month	At 6 Months	At 12 Months

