m = No. of Subjects Who Had Event(s)	No. of subjects who had an event with scan day within the 1-month window.	No. of subjects who had an event with scan day within the 6-month window.	No. of subjects who had an event with scan day within the 12-month window.
n = No. of Subjects Who Had Readable Images	No. of subjects who had a readable image within the 1-month window.	No. of subjects who had a readable image within the 6-month window.	No. of subjects who had a readable image within the 12-month window.
Event rate = m/n	Through 1 Month	Through 6 Months	Through 12 Months
m = No. of Subjects Who Had Event(s)	No. of subjects who had an event with scan day within the 1-month window.	No. of subjects who had an event with scan day within 1- or 6-month windows.	No. of subjects who had an event with scan day within 1-, 6- or 12-month windows.
n = No. of Subjects Who Had Readable Images	No. of subjects who had a readable image within the 1-month window.	No. of subjects who had an event (counted in m) or had a readable image within the 6-month window.	No. of subjects who had an event (counted in m) or had a readable image within the 12-month window.

The imaging based event rates by visit at 24, 36, 48 and 60 months will be calculated in a similar way as above; i.e., m = number of subjects who had an event with scan day within the statistical analysis window of the specific time point; n = number of subjects who had a readable image within the 12-month window.

The cumulative event rate through 24, 36, 48 and 60 months will be estimated using survival analysis. Kaplan-Meier estimates, along with its standard error using the Greenwood method, will be reported for non-image based events. The image-based events are interval censored data and the interval censored survival analysis method will be used to calculate the event rates.

When reporting the site reported endoleaks, both site imaging findings and the events treated during secondary procedures will be accounted for in the analysis.

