7.10. Safety Evaluation

All adverse events (AE) will be coded using the Medical Dictionary for Regulatory Activities (MedDRA) and categorized by System Organ Class (SOC) and Preferred Term (PT) for summary. Device-related AEs, procedure-related AEs, and serious AEs will be tabulated separately and by time period. The denominator in event rate calculation will be based on the number subjects available at the beginning of each time period. The relationship to device and procedure as well as seriousness will be based on site-reported data from the AE case report form (CRF).

The survival from all-cause mortality and aneurysm-related mortality over one year time or longer will be described by the Kaplan-Meier survival curve and the associated Kaplan-Meier estimate will be calculated along with its standard error using the Greenwood method.

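### Kaplan-Meier is planned to 5 years for aneurysm-related death and non-fatal clinical events with no rule for other deaths, so on the standard reading it overstates the proportion of patients affected

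*SAP*

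**What the plan says.** - **Mortality (SAP 7.10).** One sentence covers two different endpoints: "The survival from all-cause mortality and aneurysm-related mortality over one year time or longer will be described by the Kaplan-Meier survival curve". The standard error is Greenwood's.
- **Other non-image events (SAP 7.9).** Through 1 year, mortality, secondary procedures, MAEs, SAEs, conversion and rupture use the crude proportion of Table 5. After that, "The event rates beyond 1 year through 5 years will be analyzed using Kaplan Meier method". For cumulative rates at 24 to 60 months, "Kaplan-Meier estimates, along with its standard error using the Greenwood method, will be reported for non-image based events". MDEs are a listed endpoint at those times and are not image-based, so this covers them too.
- **Image-based events (SAP 7.9).** These are handled differently: "The image-based events are interval censored data and the interval censored survival analysis method will be used to calculate the event rates".
- **Leaving the study early (SAP 7.9).** "If a subject is early terminated from the study, the last day that the subject has been seen will be the duration in study". Nothing is added for a subject who dies of an unrelated cause. Protocol F.7.1 lists death as one of the reasons for study exit.
- **Protocol H.1.** It names the method for one endpoint only: "The survival from all-cause mortality over one year time or longer will be described by the Kaplan-Meier survival curve". The extension to aneurysm-related mortality and non-fatal events comes from the SAP.
- **Definition of aneurysm-related mortality (Protocol L.2.1).** It is a subset of deaths: "Any death occurring within 30 days from either the initial procedure or any secondary procedure intended to treat the aneurysm will be considered ARM", unless evidence points elsewhere, plus deaths resulting from a procedure on the target aneurysm, from rupture or from conversion.

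**The concern.** A subject who dies of cancer at month 20 can never have an aneurysm-related death, a secondary procedure, a conversion or a rupture. If that death is treated as ordinary censoring, Kaplan-Meier assumes the subject would have gone on to have events at the same rate as the survivors. The result estimates risk in a notional population where nobody dies of anything else. Readers will take a cumulative event rate at 60 months to be the share of patients affected, and 1-KM is higher than that share whenever other deaths precede later events. Greenwood's standard error describes the same notional quantity.

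The 60-month extension was added to show long-term safety and effectiveness, to support the marketing application and to serve post-market surveillance (Protocol L.3.2). The secondary endpoints are descriptive, so the point estimate and its standard error are the whole result. The gap also grows with follow-up, so it falls on the period in which the SAP uses Kaplan-Meier.

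**Working it through.** **Is there a figure to reproduce?** No. The documents give no 5-year event rate, no other-cause death rate, and no precision target for these analyses. Both rates below are assumptions.

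**Step 1: constant hazards.** Let K be the 5-year 1-KM and D the 5-year probability of death from other causes. Put A = -ln(1-K) and B = -ln(1-D). The cumulative incidence at 5 years is

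CIF = A/(A+B) × [1 - (1-K)(1-D)].

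Example with K = 8% and D = 35%: A = 0.0834 and B = 0.4308, so A/(A+B) = 0.162. The bracket is 1 - 0.92 × 0.65 = 0.402. CIF = 0.162 × 0.402 = 6.5%.

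Example with K = 20% and D = 45%: A = 0.2231 and B = 0.5978, so A/(A+B) = 0.272. The bracket is 1 - 0.80 × 0.55 = 0.56. CIF = 0.272 × 0.56 = 15.2%.

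| 1-KM at 5 years | CIF, D = 25% | CIF, D = 35% | CIF, D = 45% |
|---|---|---|---|
| 8% | 7.0% | 6.5% | 6.0% |
| 15% | 13.1% | 12.3% | 11.4% |
| 20% | 17.5% | 16.4% | 15.2% |

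The relative overstatement at 5 years is about 15%, 22% and 32% across the three columns. At 1 year, with the same hazards, it is about 3%, 4% and 6%.

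**Step 2: events that cluster early.** Constant hazards suit these endpoints poorly. Aneurysm-related mortality takes in most deaths within 30 days of a procedure, primary conversion happens at the index procedure, and several MAEs are peri-procedural by definition. Suppose a fraction f of the cumulative event hazard A falls at day 0 and the rest is spread evenly. Then p0 = 1 - (1-K)^f, and CIF = p0 + (1-p0) × (the step 1 formula, with A replaced by (1-f)A and K by the matching late probability).

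Example with K = 20%, D = 45% and f = 0.5: p0 = 1 - √0.80 = 10.6%. The late part is 0.894 × [0.1116/(0.1116+0.5978)] × [1 - 0.894 × 0.55] = 7.1%. CIF = 17.7%, a gap of 2.3 points instead of 4.8.

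| 1-KM | Gap in points, f = 0 (D = 25/35/45%) | Gap in points, f = 0.5 (D = 25/35/45%) |
|---|---|---|
| 8% | 1.0 / 1.5 / 2.0 | 0.5 / 0.7 / 1.0 |
| 15% | 1.9 / 2.7 / 3.6 | 0.9 / 1.3 / 1.8 |
| 20% | 2.5 / 3.6 / 4.8 | 1.2 / 1.7 / 2.3 |

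With f = 0.75 the gap is about 0.3 to 0.5 points at 8% and 0.6 to 1.1 at 20%. If all events fall in the first 30 days, the overstatement is under 1% in relative terms.

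**Step 3: simulation of the two estimators.** With n = 100 and constant hazards, D = 30% and K = 10% give a mean 1-KM of 10.1% against 8.5% for Aalen-Johansen. D = 45% and K = 20% give 20.1% against 15.3%. With n = 47 the same two cases give 9.9% against 8.4% and 19.8% against 15.1%. The formula holds at these sample sizes.

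**The case against.** - **Nothing is decided on these figures.** SAP 7.9 plans no inference on secondary endpoints. The primary test is an exact binomial test on a proportion. The error makes the device look worse, not better. All of this is correct. It limits the seriousness of the point but does not make the estimate right.
- **The size is assumed.** True. A reader might take the constant-hazard gap of about 2 to 5 points at event rates of 15-20% as the expected error for secondary procedures or MAEs. The documents do not support that: they give neither rate, and step 2 shows how far early clustering shrinks the gap.
- **Sampling error is larger.** With 35% other-cause death, constant hazards and no dropout, the standard deviation of the 5-year Kaplan-Meier estimate at n = 100 is roughly 3, 4 and 4.5 points at 8%, 15% and 20%. The biases are 1.5, 2.7 and 3.6. Subjects who decline re-consent leave at 12 months (Protocol L.3.3.2), so precision will be poorer still. But this bias has a known direction and is cheap to remove.
- **A net failure probability is a recognised measure of device durability.** Fair, and a reason to keep Kaplan-Meier as a supportive table. The SAP does not say that this is the quantity it wants. The remark on Greenwood's standard error follows from the same choice and is not a second defect.
- **The censoring rule is inferred.** Also true. The SAP refers to the US trial protocol for clarification, and that protocol is not among the documents. Nothing in the two documents points to another rule.
- **Scope.** A reader might infer that every time-to-event endpoint needs changing. It does not. Image-based events use an interval-censored method, and ordinary Aalen-Johansen needs observed event times. An adverse event that leads to death is itself an SAE (Protocol F.6.1), so SAE rates have essentially no competing death. MAEs are missing from the 24-60 month lists in Protocol L.3.3.1 and SAP 7.9, although the protocol synopsis and the SAP's method sentence can be read to include them. They belong here only if reported.

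**Conclusion.** The point holds for aneurysm-related mortality, MDEs, secondary procedures, conversion, rupture and, if reported, MAEs beyond 1 year. The SAP specifies Kaplan-Meier with no rule for other deaths. On the standard reading, 1-KM is never below the proportion of patients affected, and exceeds it once other deaths precede later events.

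The size cannot be derived from the documents. Under constant hazards and an assumed 25-45% other-cause death at 5 years, the overstatement is about 1 to 2 points at a 1-KM of 8% and 2.5 to 4.8 points at 20%. It is about half that if half of the events are peri-procedural, and negligible if nearly all are.

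All-cause mortality is unaffected, and so are the 30-day and 1-year hypothesis tests. A reader might infer that the long-term results are invalid or that a success criterion is at risk. Neither follows: this is an upward bias in descriptive estimates. It is worth correcting because those estimates are the main product of the extended follow-up.

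**What to change.** In SAP 7.9 and 7.10:

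1. Keep Kaplan-Meier with Greenwood's standard error for all-cause mortality.
2. For aneurysm-related mortality, MDEs, secondary procedures, conversion, rupture and (if reported) MAEs beyond 1 year, report the Aalen-Johansen cumulative incidence with its own standard error.
3. State the rule for deaths: a death that does not itself count as the event is a competing event, not a censoring. For aneurysm-related mortality, that means any death adjudicated as unrelated to the aneurysm. For MDEs, it means a death that is not device-related in a subject with no earlier MDE. For secondary procedures, conversion and rupture, it means a death before the event.
4. Keep the Kaplan-Meier figures for these endpoints as a supportive table, for comparison with older device reports.
5. Leave SAE rates and the interval-censored imaging analyses outside this change, and say whether MAEs are reported beyond 12 months.

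No new data are needed. Event onset and death dates are already used in the analysis, and the Clinical Events Committee adjudicates all deaths (Protocol F.6.6). The cost is some SAP wording and one extra set of estimates, with less direct comparability with historical Kaplan-Meier reports unless both are shown. The rule should be fixed before the long-term data are analysed, because SAP section 3 describes the plan as flexible and a later choice of estimator could look selective.

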7.11. Health Outcomes Analyses

Health-related quality of life outcomes will be assessed at all scheduled follow-up visits using the EQ-5D questionnaire. For each dimension of EQ-5D score, a frequency table will be presented. For visual analogue scale score, EQ-5D Index and change from baseline in EQ-5D Index, number of subjects with known value, mean, standard deviation, median, minimum and maximum will be reported. The scoring algorithm by Shaw JW *et al* (2004) will be used to compute the US preference-weighted index score.

8. Validation Requirements

Level I validation is required for each computer programmed table and listing used in the PMA and PMA-s submissions.

9. References

